## **10) Risks/Benefits**

This study is a prospective cohort study that will collect private, identifiable information about human subjects. The main risk is to subjects' confidentiality should an individual outside of the study team access the study data.

There may be no direct benefit to subjects.

The group receiving the postoperative nerve block may have better pain control and less opioid use.

This research might lead to the benefit of others should the analysis of the data lead to better selection of surgical candidates and possible interventions to reduce adverse outcomes.

## **11) Adverse Events / Serious Adverse Events**

Any untoward or unfavorable medical occurrence in a human study participant, including any abnormal sign (e.g. abnormal physical exam or laboratory finding), symptom, or disease, temporally associated with the participants' involvement in the research, whether or not considered related to participation in the research will be recorded for the first 24 hours post-operatively.

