## 5) Procedures Involved\*

Study design: All patients who fulfill inclusion criteria, including undergoing a pregnancy test if a woman of childbearing age, undergoing total knee arthroplasty will be randomized to one of two groups to be given the standard orthopaedic joint replacement protocol including general anesthesia with the preoperative adductor canal block **or** the standard orthopaedic joint replacement protocol including general anesthesia except the adductor canal block will be given at the end of the procedure instead of the beginning. General anesthesia for the groups will be standardized, and no intraoperative analgesics given. Nerve blocks will be placed for both groups by anesthesiologists as is the standard protocol. All nerve blocks will be placed following the same procedural protocol with the same supplies under ultrasound guidance to ensure consistency and minimize variation. Nerve blocks in both groups will include the standard 20mL Ropivacaine 0.2% (local anesthetic) injected in the same manner. PACU orders will not differ between the groups and will be the standard procedure for total joint arthroplasty at the facility. Cases will be assigned randomly in a 1:1 fashion. A computer program such as Microsoft Excel will be employed for the randomization process.

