**6-Oxycodone 5mg every 4 hours as needed for pain during the first 1-2 weeks postop**

After surgery, patients will be evaluated for the primary outcome of pain status at time points 2 hours and 24 hours using the numeric rating pain scale (0-10). Patient's nausea and vomiting will be evaluated by using a binary "yes" or "no" for nausea and recording the number of episodes of vomiting. The Apfel score will be used during statistical analysis to explore possible causes for differences in nausea and vomiting (0-4). Opioid consumption will also be recorded during the first 24 hours and converted to morphine milliequivalents using patient medical records. Patient data will then be compiled for statistical analysis.

Patients will be assessed routinely once every hour by the circulating nurse for the duration of their care in the hospital. Should a patient receive ambulatory care and depart from the hospital before 24 hours have elapsed, they will be contacted via telephone for assessment using the numeric rating pain scale (1-10) and post-op nausea and vomiting.

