## **6) Study Timelines\***

- *Participants will be active in the study for the 24 hours after the index knee replacement surgery.*
- *It will take about 6 months from the start of the study to recruit the total anticipated participants.*
- *We will allot 1 month after the final participant has completed the study for analysis and write up.*

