## **7) Study Design**

- The primary purpose of this project is in the treatment of pain around the immediate post-operative time after total knee replacement surgery. As a parallel experimental/interventional study design, patients will be randomized to either the control group (institution specific joint replacement pain protocol) or the intervention group (receiving the postoperative adductor canal block). Patients and those collecting the postoperative data will be blinded to eliminate bias in a 1:1 randomization process matching intervention group patients with control group patients. The surgeon will not be informed

ahead of time regarding which cohort a patient belongs to in an effort to reduce bias, though during the procedure may become privy to the group due to when the anesthesiologist places the block. The anesthesiologist will be informed the night before the respective procedure as to which group the patient was randomized into by one of the other non-primary surgeon members of the team. The randomization will be done using a random number generator. We aim to enroll 84 patients. If interested, the subject will be allowed to find out their group assignment when the study is over.

- Power Analysis:

Study Group Design: Two independent study groups

Primary Endpoint: Continuous

Data normally distributed

Alpha: 0.05

Power: 0.80

Total number of patients enrolled: 84

Based on similar study design [10], the standard deviation for pain scores was 3. Assuming a reasonable clinically significant difference of 2 on VAS score, this calculates to sample size of 35 in each group. Assuming attrition rate of 20%, 42 samples in each group will be obtained

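### Adverse events are recorded only after surgery, although the arms differ in whether the block comes before surgery or at its end, so early block events are captured unequally by arm

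*Combined protocol and SAP*

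**What the plan says.** Section 11 defines an adverse event broadly, as any unfavourable occurrence "temporally associated with the participants' involvement in the research, whether or not considered related to participation in the research". It then limits collection in time: such events "will be recorded for the first 24 hours post-operatively". Section 6 sets the same horizon for participation: "Participants will be active in the study for the 24 hours after the index knee replacement surgery".

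Section 5 describes the two arms. Control patients receive "general anesthesia with the preoperative adductor canal block". For intervention patients, "the adductor canal block will be given at the end of the procedure instead of the beginning". Agent, volume and technique are otherwise the same, and allocation is 1:1.

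Section 5 also provides for nursing checks: "Patients will be assessed routinely once every hour by the circulating nurse for the duration of their care in the hospital". This sentence stands with the pain, nausea and vomiting assessments. It is not described as adverse-event collection, and it does not say that the checks start at the block.

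Section 8 lists no safety endpoint, and Section 9 plans no comparison of adverse events between arms.

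**The concern.** The adverse-event window is tied to surgery, while the randomised factor is the timing of the block relative to surgery. Measured from the block, the two arms are therefore observed over different periods. In the intervention arm, observation begins at or shortly after the block. In the control arm, it begins only after the whole operation has passed. A short-lived complication of block placement could be counted in one arm and missed in the other even if its true frequency is the same.

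What is at stake is the safety description that would accompany the efficacy result. If the report lists adverse events by arm, the counts will partly reflect the recording rule and not only the effect of block timing. The operation itself is also outside the window. In the intervention arm, that is the period during which the patient has no block in place, so a consequence specific to the intervention could go unrecorded as well.

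**Working it through.** **1. The windows, measured from the block.** Let D be the time from the pre-operative block to the end of surgery. The plan does not give D.

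- Post-operative block (Section 5, end of procedure): the window runs from about 0 to 24 h after the block.
- Pre-operative block (Section 5): the window runs from about D to D + 24 h after the block.

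The first D hours after the block are thus outside the window in one arm and inside it, or nearly so, in the other.

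**2. Does another section widen the window?** Section 6 does not, since active participation is the 24 hours after surgery. The hourly checks in Section 5 do not, for the reasons given above. The broad definition in Section 11 widens what counts as an event, but its last clause still fixes when events are recorded. No section provides for recording from randomisation, from block placement or during the operation.

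**3. Which events are lost?** Section 11 records events whatever their cause. An effect of the pre-operative block that first appears after surgery, or is still present then, is recordable. Only events that both start and resolve before the window opens are lost.

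**4. Illustration.** The plan gives no adverse-event rate, so these inputs are assumptions except for the arm size.

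- Arm size: 84 / 2 = 42 (Section 7).
- p: true risk of a block event, the same in both arms, taken as 1% to 10%.
- f: share of pre-operative block events confined to the time before surgery ends.

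Expected recorded events are 42p(1 - f) in the pre-operative arm and at most 42p in the post-operative arm.

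| p | Post-operative arm (upper limit) | Pre-operative, f = 0.25 | Pre-operative, f = 0.5 | Pre-operative, f = 1 |
|---|---|---|---|---|
| 1% | 42 × 0.01 = 0.42 | 0.315 | 0.21 | 0 |
| 5% | 42 × 0.05 = 2.1 | 1.575 | 1.05 | 0 |
| 10% | 42 × 0.10 = 4.2 | 3.15 | 2.1 | 0 |

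**5. Why the post-operative column is an upper limit.** Section 11 does not define when the post-operative period starts, and the intervention block is given at the end of the procedure. If the clock starts later than that block, a share g of its events is lost too. The expected difference is then 42p(1 - g) - 42p(1 - f) = 42p(f - g), which shrinks as g approaches f.

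**6. Events not caused by the block.** Other events that begin and end during surgery are missed in both arms. If their risk is the same in both arms, this adds no imbalance. If it differs because one arm has surgery without a block, the omission could offset or add to the difference in step 5. The plan gives nothing from which to judge this.

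**The case against.** The strongest defence is that little in the trial depends on this record. Adverse events are not an endpoint and no between-arm test of them is planned. The pain, opioid, nausea and vomiting, and length-of-stay results are untouched. That is correct, and it limits the point to descriptive safety reporting.

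A second defence is that the definition in Section 11 is broad enough to capture lasting effects of either block. That also stands. A reader might infer that everything caused by the pre-operative block escapes recording, and so expect none recorded against about two at a 5% risk. The documents do not support this. It is the f = 1 row-end of the table, where every event resolves before surgery ends, and the 5% is itself an assumption. At f = 0.25 the same risk gives about 1.6 against at most 2.1.

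A third defence is that, with no defined time zero, immediate events of the end-of-procedure block may fall outside the window too. This is possible and makes the size of the imbalance less certain. It does not rescue the rule, because an undefined start is a further gap in it.

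Finally, events during surgery may well be noted in routine clinical records. The plan does not say that they will be collected as trial adverse events, and that is what matters for the safety report.

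**Conclusion.** The point holds in limited form. Adverse-event ascertainment differs by arm because the window opens after surgery while the arms differ in block timing. Events confined to the time between the pre-operative block and the end of surgery are missed. The same early events after the end-of-procedure block can be recorded, and events that appear or persist after surgery are recorded in both arms.

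For immediate block events the likely effect is to make the post-operative block look worse. The net direction is uncertain, given the unrecorded intra-operative period and the undefined start of the window. The expected difference is at most 0.42 to 4.2 events for an assumed risk of 1% to 10%, and that maximum needs f = 1 and full capture in the post-operative arm. The illustration also assumes equal true risk in both arms and 42 blocks given in each.

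A reader might further infer that the trial would recommend a block time on a biased safety record. Nothing in the plan says that its conclusions will rest on adverse events. The primary analysis and the sample size are unaffected. The change is worth making because it is cheap and because Section 11 is the sole basis for any safety statement.

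**What to change.** In Section 11, record adverse events in both arms from one common time point that precedes either block, for example arrival in the pre-operative area on the day of surgery, to 24 hours after a defined end of surgery. Report them by arm. State which recorded time marks the end of surgery, and bring the participation period in Section 6 into line.

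The start should not be tied to block placement or to the start of anaesthesia, whichever comes first. That moment can itself differ by arm and would bring back part of the problem.

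The cost is a sentence or two of text and slightly more record abstraction; Section 5 already plans to use medical records for opioid data. No treatment, endpoint or sample size changes.

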## **12) Setting**

Single center study - University of Miami Hospital

